Growing evidence supports that physical functional limitations can be a cause and result of urinary incontinence in aging adults. Tinetti et al studied a cohort of older community dwelling adults (N=927) to assess predisposing factors associated with UI, falling, and functional dependence. They reported that lower extremity weakness revealed by abnormal performance on timed chair stands showed the strongest relationship.(3) Erikson et al. further clarified this relationship in a secondary cross-sectional analysis that revealed that among women with daily UI, 24% reported specific difficulty or dependence with using the toilet and had 3.3 increased odds of functional difficulty or dependence compared to continent older women.(2) There is great need for revising non-surgical interventions for UI in older women with physical function limitations as the development of functional dependency is an important adverse outcome of UI among older adults.(8) Urinary urgency incontinence has been independently associated with risk of falling [OR 1.26 (1.14-1.40)] and non-spine nontraumatic fractures [relative hazard 1.34 (1.06-1.69)].(9) In addition, UI was experienced by 24% of women older than 65 years who participated in the California Health Interview Survey and was significantly associated with poorer overall health (adjusted OR 3.43), decreased mobility (OR, 1.81), and history of falls (OR, 1.53).(10) Understanding the relationship between physical function and UI is critical to effectively treat these conditions as they often occur concomitantly. Sarcopenia may be an important factor contributing both to UI and functional decline in older women and may explain how these two conditions are associated. Women >60 years with stress UI experienced increased pelvic floor muscle strength and functional efficiency with a decline in UI episodes after 12 weeks of intensive pelvic floor physical therapy.(11)

However, only 44% independently adhered, and this has been related to weak muscle function at baseline. Recent reports that UI episodes decrease with increased physical activity (walking) and group based physical fitness in institutionalized older women support our hypothesis that muscle function beyond the pelvic floor is important and needs to be characterized to improve the efficacy of non-surgical therapy for treatment of UI.(12, 13)

Objectives:

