(Defined by the QUID assessment as having subscale score for stress ≥ 4 , and/or urge score ≥ 6 , and/or total QUID score ≥ 10)
 - c) Willing and able to be compliant with pelvic floor muscle exercise intervention (standard of care) for 12 weeks and to log compliance
 - d) Willing and able to undergo an extensive physical function evaluation
 - e) SPPB ≤ 9 (for any new screens conducted after amendment 12 is approved)
- **Exclusion criteria:**
 - a) Prior surgical intervention for urinary incontinence within the past 12 months
 - b) Hysterectomy within 12 months
 - c) Having primarily nocturia
 - d) Diagnosis of:
 - i) Pelvic Organ Prolapse beyond the hymenal ring
 - ii) Urogenital Fistula
 - iii) Neurogenic Overactive Bladder (associated with a diagnosis of Multiple Sclerosis or Stroke within past 12 months)
 - iv) Incomplete Bladder Emptying/Urinary Retention with PVR >150 ml (measured by bladder scan)
 - e) Wheelchair bound
 - f) Having significant cognitive impairment or dementia
 - g) Unsafe to exercise (severe cardiopulmonary disease)
 - h) Unable/unwilling to provide informed consent
 - i) Determined otherwise ineligible by the principal investigator

Sample Size Estimate:

With 50 women per group (functional impaired and non-impaired) and assuming a drop-off rate of 15% for a two-sided test, we will be able to detect a 20% difference of improvement of UI episodes (assuming a standard deviation of 32%)[40] with at least a power of 80% at 0.05 significance level for Aim 1.

Interventions and Interactions:**Interaction 1: Mailing of Introductory Letters**

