Study introductory packets will be mailed to all women who qualify for participation. These will include the consent form, study related questionnaires, and an introductory letter with details of the upcoming study visit. We may bring people in for a separate pre-screen visit to assess their SPPB score prior to scheduling them for a full study visit 1 since as of amendment 12, the SPPB is part of the eligibility criterion.

Interaction 3 (Study visit 1): (Average duration 3 hours)

Enrollment will take place at the Geriatric Clinical Research Unit in our Claude D. Pepper Older Americans Independence Center supported by the Wake Forest CTSI. A study staff member will confirm eligibility, describe the study, answer any questions, and administer written informed consent.

- A. Demographic and medical characteristics:** age, parity, mode of delivery, history of hormone replacement therapy use, history of vaginal estrogen use, anthropometric body measurements.
- B. Overall health status** and 10-year mortality risk will be assessed using the Charlson Co-morbidity Index. [19] Self-reported health status will be assessed using the Medical Outcomes Study Short-Form 36 (SF-36). [20]
- C. Emotional health** will be determined using the Center for Epidemiologic Studies Depression (CESD). [21]
- D. Pelvic floor assessment:** All participants will undergo a pelvic examination (to evaluate for urogenital atrophy and vaginal prolapse) and pelvic floor muscle assessment performed by the PI or a pelvic floor physical therapist. These assessments are a routine component of the pelvic floor assessment performed by these practitioners during an evaluation for pelvic floor symptoms.

Participants are placed in the supine position with 1-2 pillows to support the head. Next, the hips are flexed and the abducted and the knees are bent. Use of stirrups may be helpful. A single finger (index) is placed 4-6 cm inside of the vagina and positioned at either 4 or 8 o'clock to monitor muscle activity. Moderate pressure may be applied to the muscle bulk to assist in the initiation of the appropriate muscle contraction.

The PERFECT scheme will be applied for baseline and follow-up pelvic floor assessment. The PERFECT scheme is a valid and reliable pelvic floor assessment tool to assess pelvic floor muscle strength and efficiency. [22] PERFECT assessment includes the following measures:

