J. Cognitive function will be assessed using the Montreal Cognitive Assessment (MoCA). Mild cognitive impairment will be defined as MoCA score of <26. Severe cognitive impairment will be determined by MoCA score <21.[38]

At the conclusion of the Study Visit 1, participants are given a folder labeled with their study ID. The folder will contain the following:

- Voiding diary (toilet hat should accompany this)
- Pelvic floor muscle exercise compliance log (we explain that this is an observational study, therefore, they should only complete the log reflecting what they actually are able to do at home)
- Copy of informed consent form
- Label indicating the time/day of their next appointment

- Sheet cover insert containing the bladder diary OR questionnaires necessary for the upcoming study visit 2 (bladder diary), study visit 3 and 4 (Questionnaires and bladder dairy)

All assessments will be repeated during the 6- week follow-up visit. Questionnaire based assessments and UI voiding diaries will also be repeated at week 12. (see *Appendix Table 1 – Assessment schedule*)

*We were mailing the questionnaires, but they would invariably reach the participants in time. Therefore, we are modifying our technique to increase compliance with completing the questionnaires and improve the efficiency of study visits.

Study visit 2 (week 2): (20 minutes) This visit will ensure that pelvic floor muscle strength and contractions are being performed and recorded correctly. The PI will assess each participant by performing a digital vaginal exam, to confirm proper isolation of pelvic floor muscles and ability to complete the PFME prescription. The bladder diary will be reviewed, clarified, and collected. A data abstraction form should be completed at this time. The pelvic floor exercise prescription may be modified at this visit, if that occurs, a new document will be provided and the previous prescription will be stored in the participants chart. The PFME compliance log should be reviewed. A brief visit note should be completed to summarize the events.

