The hypothesis for AIM 1 (Primary) will be tested using analysis of covariance (ANCOVA) to compare differences of efficacy of PFME therapy (i.e. % UI episodes/week reduction at week 6) between women with and without functional impairment, adjusted for age, race/ethnicity, and BMI. Differences in least-squares means and associated 95% confidence intervals will be calculated. For Sub-aim 1(a), attitudes (barrier and motivation) towards physical activity will be compared between higher vs. lower physically active women using Chi-Square tests. For Sub-aim 1(b), association between physical activity (lower vs. higher) and UI severity will be tested using logistic regression, adjusting for age, race/ethnicity and BMI. Odds ratio and associated 95% confidence intervals will be calculated. We will also explore the impact of functional impairment on the association by adding an interaction of functional impairment and UI severity. Similar ANCOVA models as for Aim 1 will be used to compare efficacy of PFME therapy between women with and without sarcopenia (AIM 2) and between women with and without mild cognitive impairment (Aim 3).

Potential Pitfalls and Alternative Solutions:

- a) **Recruitment:** Women will be recruited from the community in the catchment area for Wake Forest Baptist Health system, which includes central and western North Carolina and south central Virginia. Last year, we saw 476 women with a urinary incontinence diagnosis. More than 30% of women older than 70 have UI symptoms and an equal number will have functional impairment. Therefore, we do not expect difficulty in recruiting 50 eligible women/year over 24 months. The Wake Forest Sticht Center on Aging has an established database of older volunteers for aging-related research (VITALS database=12,600) that will also be a source of recruitment. If necessary, we may start targeted recruitment to ensure that ~ 50% of potential participants have a SPPB score > 10 and that 50% have scores of ≤ 9 .
- b) **Adherence to PFME therapy:** Participants will receive a calendar with their PFME prescription on it and places on the calendar to document compliance. They will be contacted by study staff every 2 weeks to assess for compliance and to reinforce adherence to therapy. This approach has resulted in good compliance in other trials of elderly adults run by the Sticht Center.

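### The function contrast leaves out baseline cognition and comorbidity, so it cannot by itself support the claim that functional impairment independently predicts PFME efficacy

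*Combined protocol and SAP*

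**What the plan says.** The aims are numbered differently in Objectives and in the Analytical Plan. The function comparison is Aim 2 in Objectives and Aim 1 (Primary) in the Analytical Plan.

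- **Claim.** Objectives, Hypothesis 2, expects functional impairment and sarcopenia to predict PFME efficacy independently. Aim 2 there speaks of their impact on efficacy.
- **Design.** Study Design describes a prospective cohort grouped by physical function. Nothing is randomised.
- **Primary model.** Under Analytical Plan & Statistical considerations, the hypothesis "will be tested using analysis of covariance (ANCOVA) to compare differences of efficacy of PFME therapy (i.e. % UI episodes/week reduction at week 6"), and the comparison is "between women with and without functional impairment, adjusted for age, race/ethnicity, and BMI".
- **Comorbidity.** Interaction 3 (Study visit 1), item B: "10-year mortality risk will be assessed using the Charlson Co-morbidity Index". The Analytical Plan gives this index no use.
- **Cognition.** Interaction 3, item J: "Cognitive function will be assessed using the Montreal Cognitive Assessment (MoCA"). A MoCA score below 26 defines mild impairment. The Analytical Plan uses cognition only as an exposure in its own right, comparing efficacy "between women with and without mild cognitive impairment (Aim 3").
- **Exclusions.** Significant cognitive impairment or dementia, and severe cardiopulmonary disease, are excluded under Subject selection criteria.

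**The concern.** In a cohort grouped by function, women with more illness or lower cognition may be over-represented in the impaired group. They may also learn or keep up the exercises less well. If both hold, a model "adjusted for age, race/ethnicity, and BMI" credits function with part of an effect that belongs to general health or cognition. The error runs in the direction Hypothesis 2 predicts, so a spurious result would look like confirmation.

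For cognition the gap is internal to the plan, which considers mild cognitive impairment a possible determinant of PFME response. It then examines function and cognition in parallel models, with no stated adjustment of either for the other. If the two overlap, both analyses can report the same effect, each as its own. For comorbidity the support is weaker. The background reports UI as "significantly associated with poorer overall health (adjusted OR 3.43), decreased mobility (OR, 1.81"), which links health and mobility to having UI, not to exercise response.

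At stake is the interpretation of the main result, namely whether the difference belongs to function.

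**Working it through.** **Inputs from the document (Sample Size Estimate):** 50 women per group, 15% drop-off, difference 20 points, SD 32 points, two-sided 0.05, power at least 80%.

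**Inputs by assumption (the document gives none):** each factor differs by d = 0.5 SD between groups and correlates r = 0.2 with percentage reduction, taken as the slope per SD. The two effects add, and function has no true effect.

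**1. Reproduce the plan's power.** n = 50 × 0.85 = 42.5 per group. SE = 32 × √(2/42.5) = 6.94. Power = Φ(20/6.94 − 1.96) = Φ(0.92) = 82% (81% with the t distribution). The stated figure holds.

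**2. Spurious difference if both factors are unrelated to the planned covariates.** Bias per factor = d × r × 32 = 0.5 × 0.2 × 32 = 3.2 points. For two factors it is 6.4 points, or 6.4/20 = 32% of the target. False rejection = Φ(6.4/6.94 − 1.96) + Φ(−6.4/6.94 − 1.96) = 0.150 + 0.002 = 15%. A simulation with 42 per group gave 14%.

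**3. Allow for age, which is in the planned model.** Assume age is also 0.5 SD apart between groups and correlates ρ with each factor within groups. Age adjustment then removes ρ × 0.5 of each 0.5 SD gap, so the bias becomes 6.4 × (1 − ρ).

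| ρ | Bias (points) | False rejection (SE 6.94) |
|---|---|---|
| 0 | 6.4 | 15% |
| 0.3 | 4.5 | 10% |
| 0.4 | 3.8 | 9% |

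Simulation of the last two cases gave about 4.0 to 4.7 points.

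**4. Range before any allowance for age.** With gaps of 0.3 to 0.8 SD and correlations of 0.1 to 0.3, two factors give between 2 × 0.3 × 0.1 × 32 = 1.9 points and 2 × 0.8 × 0.3 × 32 = 15.4 points. False rejection runs from 6% to 60%.

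**5. Cost of adding both scores.** Three simulated settings (42 per group, total SD 32, planned covariates not included) gave these standard errors without and with the two scores:

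| Gaps (SD) | Slopes (points per SD) | SE without | SE with | Increase | Power for 20 points, with |
|---|---|---|---|---|---|
| 0.4 / 0.4 | 6.4 | 6.96 | 7.03 | 1% | Φ(20/7.03 − 1.96) = 81% |
| 0.5 / 0.5 | 6.4 | 6.97 | 7.19 | 3% | Φ(20/7.19 − 1.96) = 79% |
| 0.5 / 0.75 | 8 | 6.96 | 7.24 | 4% | Φ(20/7.24 − 1.96) = 79% |

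If the two scores explained 20% of group membership and none of the outcome, the SE would be 6.94/√0.8 = 7.76 and power Φ(20/7.76 − 1.96) = 73%.

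**The case against.** The strongest reply is that the size is unknown and may be small. No gap or correlation comes from the document. Age and BMI are in the model and may carry part of both factors. The exclusions for dementia and severe cardiopulmonary disease narrow the range of both. All of this stands, and it is why the figure with age in the model matters more than the 6.4 points. It does not close the gap, because mild cognitive impairment remains eligible and is itself analysed.

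A second reply is that the aim is descriptive, or that independence in Hypothesis 2 means only that impairment and sarcopenia are independent of each other. A descriptive contrast by function group would be valid as planned. But Aim 2 speaks of impact, and the primary function model does not include sarcopenia either, so the narrower reading does not rescue the claim.

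A third reply is that adding both scores to the primary model could take its power below the stated 80%. This stands, and it is the reason for a second model.

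A reader might also infer that women with neurogenic bladder from an older stroke would load the impaired group. The document does not support that. The exclusion wording, "associated with a diagnosis of Multiple Sclerosis or Stroke within past 12 months", can be read as attaching the 12 months to stroke alone. The medical characteristics in item A list no neurological history, and nothing shows in which group such women would fall.

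**Conclusion.** The point holds as a limit on interpretation. The planned ANCOVA can estimate the difference between function groups given age, race/ethnicity and BMI. It cannot show that the difference is independent of cognition and comorbidity. Under the assumed 0.5 SD gaps and correlations of 0.2, the spurious difference is about 6 points if neither factor is related to the planned covariates. It is about 4 to 5 points, with 9-10% false rejection, under the age assumptions above. It may be smaller after the exclusions.

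Three stronger readings are not supported:

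- **That the primary result is known to be biased by a given amount.** Every association used here is assumed, and the link from Charlson score to PFME response is a subject-matter premise.
- **That the plan ignores cognition.** It analyses cognition, but separately.
- **That adding the two scores restores a 5% error rate.** That is true only where they are the sole confounders and are measured without error. With an assumed reliability of 70%, about 0.3 × 6.4 = 1.9 points would remain.

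**What to change.** In the Analytical Plan:

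- Keep the planned ANCOVA as the primary analysis.
- Pre-specify a second ANCOVA with the same outcome and covariates plus continuous baseline MoCA and baseline Charlson score.
- State that any claim of independent prediction by functional impairment rests on the second model, and report both estimates with 95% confidence intervals.
- Confirm that Charlson is collected at baseline. It is described under Interaction 3 but has no row in Appendix Table 1, which looks clerical.

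The cost is SAP wording, given that confirmation. The second model spends two degrees of freedom and has a standard error about 1-4% larger, with power for 20 points of about 79% rather than 82%. It would be lower if the two scores strongly predict group membership. The primary model's power does not change. The second model reduces confounding by general health and cognition but does not remove all of it, and the report should say so.

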AIM 3: To explore the relationship between obesity, attitudes (barriers, motivation) towards physical activity, and physical activity levels in a well-characterized longitudinal cohort of older women with UI symptoms. **Hypothesis 3.** Older women with UI view UI severity as a barrier to a high physical activity. Lower physical activity levels (defined as <6.2 MET hours/week) in women with UI impacts on physical performance and is associated with obesity. Physical activity levels will be determined using the Community Healthy Activities Model Program for Seniors questionnaire that reports metabolic equivalent task (MET) hours/week.(6) Questionnaires will assess barriers to and motivations for physical activity.

METHODS AND MEASURES:

Study Design:

We plan a prospective cohort study with an adaptive design based on physical function status. The design will involve tracking the number of women recruited with physical function impairment and those without any functional impairment. We aim to recruit similar numbers of women in each group. If we find unequal numbers, we will adapt our recruitment strategies based on a woman's functional status.

We will compare changes in outcome measures within and between groups after 6 and 12 weeks of PFME. The change in pelvic floor strength/efficiency will be assessed by repeating the pelvic floor PERFECT assessment and will be compared between groups. Changes in UI symptoms, symptom severity, and impact of UI symptoms on quality of life will be determined using standardized measures described above. Data analysis will define associations between changes in PERFECT measures and the change in UI episodes (based on 3-day voiding diary), severity, and type (based on QUID-7), and impact on quality of life (PFIQ-7) within and between groups. Objective measurement of lower-extremity strength will inform the relationship between lower-extremity strength, pelvic floor strength, and UI symptoms at baseline and the 6-week visit. (See Appendix Figure 1 – Study Flow Chart)

Setting:

Study visits will take place at the Sticht Center on Aging in the Geriatric Research Clinic. The study coordinator will meet the participants in the GRC to confirm eligibility, describe the study, answer any questions, and administer written informed consent.

Subject selection criteria:

- **Inclusion criteria:**
 - a) Women, age 70 years or older
 - b) Symptoms of Urinary Incontinence for greater than 6 months

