P= power (a measure of muscle strength using digital exam or manometric perineometer). Measured on an modified Oxford scale. A single digit is used to assess power. Power is measured by assessing 3 contractions of maximal effort and obtaining a mean strength measurement. Objective measurement of perineal power will be performed using a perineometer.

Grade 0	No discernible muscle contraction
Grade 1	A flicker of pulsation is felt under the examiner's finger
Grade 2	An increase in tension is detected, without any discernible lift
Grade 3	Muscle tension is further enhanced and characterized by lifting of the muscle belly and also elevation of the posterior vaginal wall. A grade 3 and stronger can be observed as an in-drawing of the perineum and anus
Grade 4	Increased tension and a good contraction are present and are capable of elevating the posterior vaginal wall against resistance with digital pressure applied to the posterior vaginal wall
Grade 5	Strong resistance can be applied to the elevation of the posterior vaginal wall; the examining finger is squeezed and drawn into the vagina

Next, if a perineometer is tolerable, it may be placed 5 cm into the vaginal canal.

E=endurance – expressed as the length of time in seconds up to 10 seconds that the maximum strength can be maintained. When the muscle starts to fatigue, the endurance measurement is terminated. This can be felt as decreased anterior lift digitally. This can be visualized on the perineometer with decrease in calculated strength. Other indications of muscle fatigue that should cause endurance measurement to end are: contraction of hip adductors and glutei, increased contraction of transversus abdominis. Breath holding should be discouraged. If this is occurring, try to ask the participant to contract their muscles with escalation.

R=repetitions - Once fatigue is noted, the participant is given a 4 second rest before being asked to contract with the maximum amount of force again. Power and endurance is measured with each contraction up to 10. The goal of this portion is to determine the number of repetitions needed to overload the muscle. Once the participant is unable to generate the same power, the repetition count ends.

F=fast contractions – After a 1 minute break, the number of 1 second strong contractions up to 10 are counted. Participants are asked to 'contract-relax' as quickly and strongly as possible in their own time until the muscles fatigue.

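### Change in digital PERFECT scores is compared between function groups, but nothing conceals group or earlier scores from the examiner; a scoring shift that differs by group and over time could create a false difference in this secondary comparison

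*Combined protocol and SAP*

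**What the plan says.** All places are in the combined protocol and SAP.

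- **Who scores.** Study visit 1, item D, has the "pelvic floor muscle assessment performed by the PI or a pelvic floor physical therapist". Study visit 2 (week 2) has the PI repeat a digital examination of every woman.
- **How it is scored.** Under P (power), "A single digit is used to assess power", on a modified Oxford scale from 0 to 5, averaged over three contractions. Under E (endurance), timing stops at fatigue, and "This can be felt as decreased anterior lift digitally"; the text adds that fatigue can also be seen on the perineometer. The repetition count stops when the same power is no longer generated.
- **Objective measure.** Aim 2 and the outcome table plan a perineometer measurement of strength. The procedure makes it conditional: "if a perineometer is tolerable, it may be placed 5 cm into the vaginal canal".
- **How it is used.** Study Design states: "The change in pelvic floor strength/efficiency will be assessed by repeating the pelvic floor PERFECT assessment and will be compared between groups". It also relates PERFECT change to change in UI episodes, severity and quality of life.
- **What the examiner can know about group.** The design involves "tracking the number of women recruited with physical function impairment and those without any functional impairment". Interaction 2 says that "as of amendment 12, the SPPB is part of the eligibility criterion", and that a separate pre-screen visit for SPPB may be held before visit 1. Inclusion criterion (e) requires SPPB of 9 or less for new screens after that amendment.
- **What the examiner can know about earlier scores.** The exercise prescription is built from the woman's own PERFECT result. It may be changed at week 2, with the superseded one kept in her chart. Table 1 schedules PERFECT at baseline and weeks 2, 6 and 12.

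No section says that the examiner is kept unaware of function group or earlier scores, requires the same examiner throughout, or asks for an inter-rater check.

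**The concern.** Adjacent Oxford grades are separated by what a finger feels, and the end of a hold or of a set of repetitions can rest on the same judgement. The examiner may be the investigator who leads the study. If the examiner knows which group a woman belongs to and what she scored before, borderline calls at follow-up can drift differently in the two groups. That drift enters the between-group comparison of pelvic floor gain directly. It also enters the planned associations between PERFECT change and UI change. A reader could then take a scoring artefact as evidence that functional impairment limits, or does not limit, the pelvic floor response to exercise.

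**Working it through.** **1. The plan's own figure.** Sample Size Estimate: 50 per group, 15% drop-off, difference of 20 points in UI-episode improvement, SD 32, two-sided 0.05, power at least 80%.

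- Evaluable per group: 50 × 0.85 = 42.5.
- Normal approximation: power is 82.2% at 42.5 per group (81.7% at 42). With the noncentral t at 42 per group it is 80.8%.

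The stated power reproduces. It concerns UI episodes; the plan gives no such calculation for PERFECT. I take 42 per group from it for the next steps.

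**2. Which scoring error survives in a change score.** Let b(g,t) be the average scoring error in group g at time t. The between-group difference in mean change is biased by

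[b(impaired, follow-up) − b(impaired, baseline)] − [b(normal, follow-up) − b(normal, baseline)].

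An error that is the same at both visits, even if it differs by group, gives zero. So does a drift over time that is the same in both groups. Only a group-by-time shift, called b below, remains.

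**3. False-positive probability for a shift b with no true difference.** Two-sample t-test, n = 42 per group, 82 degrees of freedom, critical value 1.989:

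- SE = SD × √(2/42)
- noncentrality = b / SE
- P(p < 0.05) = P(|T| > 1.989), where T is noncentral t with 82 df

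The documents give neither the SD of change in Oxford grade nor the size of any shift. Both are assumptions: SD 0.7 to 1.1 grade, b of 0.1 to 0.3 grade.

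| SD (assumed) | SE | b = 0 | b = 0.1 | b = 0.2 | b = 0.3 |
|---|---|---|---|---|---|
| 0.7 | 0.153 | 5% | 10% | 25% | 49% |
| 0.9 | 0.196 | 5% | 8% | 17% | 33% |
| 1.1 | 0.240 | 5% | 7% | 13% | 24% |

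Worked example: SD 0.7, b = 0.3. SE = 0.7 × √(2/42) = 0.153; noncentrality = 0.3 / 0.153 = 1.96; probability 0.49.

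**4. What the shift is compared with.** The smallest observed difference that reaches significance is 1.989 × SE, which is 0.30 grade at SD 0.7 and 0.48 grade at SD 1.1. A shift of 0.3 grade is thus about as large as the significance threshold at the lower SD, and well below it at the higher.

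**The case against.** The strongest case on the other side has five parts.

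- **The plan already has an objective measure.** True, and it is the best available safeguard. But it depends on tolerability, the definition of power allows either the digital or the manometric method, and Study Design names PERFECT for the group comparison without saying which reading leads.
- **The primary outcome is untouched.** This stands. The Analytical Plan's primary analysis uses percent reduction in UI episodes at week 6, which comes from the participant's own diary, and it specifies no test for PERFECT change.
- **The bias has no stated direction.** This stands. A reader might infer that Hypothesis 2 pulls scores in favour of functionally normal women. That hypothesis states a direction for UI episodes only, and a shift can run either way: under-scoring impaired women at baseline alone would inflate their gain.
- **Knowledge of group is possible, not established.** This stands. A reader might infer that the examiner always has SPPB before visit 1. The pre-screen visit is only something that may happen, eligibility is confirmed by a study staff member, and no section says that results go to the examiner. The plan is silent rather than openly unmasked.
- **Masking now could do harm.** New screens all have SPPB of 9 or less, so masking introduced now would fall mainly on impaired women, and scoring method would be confounded with group. Nor can test order hide a group already established at visit 1. Both stand, so masking alone is not enough.

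The plan also calls PERFECT valid and reliable. That does not answer a concern about what the examiner knows when scoring.

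**Conclusion.** The concern holds, within limits. The between-group comparison of PERFECT change rests partly on examiner judgement, and nothing in the plan conceals function group or earlier scores. Under the assumed SD of 0.7-1.1 grade and 42 women per group, a group-by-time scoring shift raises the false-positive rate from 5% to 7-10% (0.1 grade), 13-25% (0.2 grade) or 24-49% (0.3 grade). The inflation is modest at 0.1 grade and becomes material from about 0.2.

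These figures show what such a shift would do. They do not estimate a bias that is present, and they do not apply to a constant rater offset. The point concerns a secondary comparison and its associations with UI change. A reader might infer that the main efficacy result is at risk; the documents do not support that. The change is worth making because it is cheap and the main safeguard is already planned.

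**What to change.** 1. **Lead with the perineometer.** Name its reading as the main between-group measure of pelvic floor strength and treat the digital PERFECT grades as supportive. Report, by function group, how many women lack a reading because it was not tolerable.
2. **Score first, release afterwards.** At every visit where PERFECT is scored, including week 2, enter the scores on a form that shows no earlier PERFECT scores and no SPPB, grip or gait results. Release these to the examiner only after entry and before the prescription is reviewed.
3. **Record examiner and masking status.** For each assessment, note who scored it and whether it was masked. Because women screened after amendment 12 all have SPPB of 9 or less, show the digital-grade comparison by masking status, or with masking status as a covariate.

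**Cost.** A revised form, two extra data fields and a sentence in the Analytical Plan; no added staff, procedures or visits. Masking will be incomplete, because mobility is visible and an examiner may remember a woman. Perineometer data will be missing for those who cannot tolerate it. If masking status and function group overlap heavily, adjustment will separate them poorly, which is a further reason to let the perineometer lead.
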